Long-course antibiotic therapy for UTIs is intended to target the uropathogens, such as *E. coli*, but also alters the micro-ecology of the intestinal flora and its antibiotic resistance pattern, leading to prolonged colonization with antibiotic resistant *E. coli* that may persist for months [22]. This not only affects the individual child, but other community members as well. Studies have demonstrated that colonization with antimicrobial-resistant *E. coli* predisposes individuals who develop UTI to be infected with a resistant strain [23, 24]. Colonization with antimicrobial-resistant *E. coli* can be spread from the one child to the other within day care centers and from day care center contacts to household members [25-28]. Thus, children in day care represent a significant reservoir of potential resistant pathogens and day care attendance facilitates broad transmission throughout a community, expanding the numbers of individuals at risk of infection due to a resistant organism.

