9.2.3 Specimen Preparation, Handling, and Shipping

9.2.3.1 Instructions for Specimen Preparation, Handling, and Storage

Urine

A urine specimen will be collected for urinalysis and culture at the Test of Cure visit. If a urine specimen is not able to be collected for asymptomatic subjects, the Study Nurse/Nurse Practitioner/Physician will attempt to collect a urine specimen at the Outcome Assessment Visit. A urine specimen will also be collected at any time during study enrollment if the child presents with UTI symptoms.

Urine specimens will be collected by various methods depending on the age of the subject and the symptoms, as detailed in the table below.

Table 6: Urine Specimen Collection by Age and Symptom Status

Child Age and Status	Method of Urine Collection
Asymptomatic infants and young children	Bag technique
Asymptomatic toilet trained children	Clean catch technique
Symptomatic infants and young children	Clean catch or catheterize
Symptomatic toilet trained children	Clean catch technique

Urine specimens for local analysis will be delivered to the site’s microbiology laboratory within one hour of collection, or kept in a box containing ice cubes, or refrigerated until delivered to the lab.

If an asymptomatic child does not urinate during the allotted TOC Visit time period, the Nurse will request additional time from the parents, but if they are not able to have the study visit continue, then the nurse will attempt to collect a urine specimen at the Outcome Assessment Visit on Day 24 - 30.

Stool samples

A stool specimen to determine antimicrobial resistance will be collected at all three study visits. Stool specimens will be collected either by inoculation of a sterile dacron-tipped swab into stool in a diaper, or by insertion of a swab into the distal rectum (similar to obtaining a rectal temperature) where it will be held in this position for five seconds. The rectal swabs or stool samples for both clinical sites will be tested, stored, and shipped to the Infectious Disease Research Laboratory (IDRL) at Children’s Hospital of Pittsburgh (PITT). These samples will be analyzed at a central lab to determine the presence of antimicrobial resistance in isolates of *E. coli* and *K. pneumonia*.

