The secondary outcome measures of this trial are provided above. A difference between the two arms with regards to asymptomatic bacteriuria, presence of clinical symptoms, and negative urine culture is not expected. No difference will mean that shorter courses of antibiotics for treatment are not inferior to long courses in eradicating bacteria from the urinary tract as well as impacting clinical symptoms. This analysis will be a conventional test for efficacy and will consist of a straightforward two-sample test for a difference between proportions, using a two-sided chi-square test at significance level of .05.

Sub-study Analysis:

Seattle Children’s Hospital R21

As previously noted, patient stool samples will be collected on 3 occasions. For primary analysis, cross-sectional analysis will be performed, i.e. looking at samples from one occasion at a time.

For each occasion, the following proportions will be summarized:

- 1) Among all patients, proportion of patients with *E. coli* detected, proportion of patients with *K. pneumoniae* detected, and same proportions within each treatment arm.
- 2) Among patients with *E. coli* detected, proportions of sub-type 0 or sub-type 1; among patients with *K. pneumoniae* detected, proportions of the two sub-types, and same proportions within each treatment arm.
- 3) Among patients with *E. coli* detected, proportions of treatment-susceptible *E. coli*; among patients with *K. pneumoniae* detected, proportion of treatment-susceptible *K. pneumoniae*; and same proportions for different treatment arms.
- 4) Among patients with *E. coli* detected AND treatment-susceptible, proportions of sub-type 1; among patients with *K. pneumoniae* detected AND treatment-susceptible, proportions of sub-type 1; and same proportions for different treatment arms
- 5) Among patients with *E. coli* detected proportion of treatment-resistant *E. coli*; among patients with *K. pneumoniae* detected, proportion of treatment-resistant *K. pneumoniae*; and same proportions within different treatment arms.

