4.2.3 Secondary analysis

The secondary endpoints include:

- a. The proportion of children experiencing a recurrent urinary tract infection at any time after the TOC visit.
- b. The proportion of children with asymptomatic bacteriuria at the TOC visit.
- c. The proportion of children that develop the gastrointestinal colonization of antimicrobial resistant *Escherichia coli* (*E. Coli*) and *Klebsiella pneumoniae* (*K. Pneumoniae*) assessed through Outcome Assessment visit (Day 24-30).
- d. The proportion of children presenting with clinical symptoms that may be related to UTI prior to or at the TOC visit.
- e. The proportion of children with positive urine culture prior to or at TOC visit.

The secondary analysis for recurrent infection (Table 5 in Section 7.1), asymptomatic bacteriuria (Table 6 in Section 7.1), presenting with clinical symptoms (Table 7 in Section 7.1), and positive urine culture (Table 8 in Section 7.1) (Endpoints a, b, d and e), will include conventional tests to evaluate whether the proportions between two treatment arms are equal. These tests will be conducted by calculating the two-sided 95% confidence limit for the difference between the short-course and standard-of-care therapies. Analyses will be performed on per-protocol population, with appropriate exclusions of treatment failures. Details of these exclusions are shown in Section 5.1.

The secondary analysis for proportion of children that become colonized with antibiotic-resistant *E. coli* and *Klebsiella pneumoniae* assessed through Outcome Assessment visit (Day 24-30) (Endpoint c) will consist of two-sample tests for differences between proportions, using a chi-square test at significance level of 0.05 (Table 9 in Section 7.1). We hypothesize that children with short-course therapy will be less likely to become colonized with emergent antibiotic-resistant *E. coli* and *K.*

pneumoniae. These analyses will examine whether antibiotic resistance after enrollment emerges differently between the short course and standard of care arms. First, a summary of antibiotic resistance present at enrollment, TOC and Outcome Assessment among the per-protocol population excluding treatment failures with a sample at TOC (Population 4) will be presented (*Table 9 in Section 7.1*).

Emergent antibiotic resistance will be defined as follows:

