Among Population 4 (per-protocol population excluding treatment failures without TOC sample), define an indicator for emergent antibiotic resistance at TOC and Outcome Assessment. A child would have emergent antibiotic resistance if they

1. Had no antibiotic-resistant E.coli or K.pneumoniae at enrollment but one or both are now present. OR
2. Had either antibiotic-resistant E.coli or K.pneumoniae at enrollment but now the other antibiotic-resistant organism is present OR
3. Had antibiotic-resistant E.coli and/or K.pneumoniae at enrollment, but have now developed resistance to new antibiotics in either organism.

Emergent antibiotic resistance will be examined by treatment arm in Table 10. We also want to show which antibiotics the organism showed resistance (ceftazidime, amoxicillin-clavulanate, TMP-SMX, or ampicillin). Prior to unblinding, patterns of multiple resistance will be summarized and if there are a few very common patterns they will also be included in this table (*Table 11 in Section 7.1*).

Longitudinal models such as mixed-effects logistic regression models and logistic regression models with generalized estimating equation (GEE) will be explored to analyze the repeated outcome of emergent antibiotic resistance.

In some cases, subjects who experienced treatment failure will not be evaluable for the secondary objectives. Specifically:

- Recurrent infection: Subjects with treatment failures will not be evaluable for recurrent infection.
- Asymptomatic bacteriuria: subjects with treatment failure will be evaluable (all will be negative for asymptomatic bacteriuria – by definition, treatment failures are symptomatic so cannot be considered to have asymptomatic bacteriuria).
- Colonization: Generally, subjects with treatment failure will not be evaluable for colonization. However, one exception would be that if the child completes the Test of Cure visit but is a treatment failure, we collect a stool specimen at that visit and thus will have a specimen to evaluate for colonization with resistant bacteria.
- Clinical symptoms: subjects with treatment failure will be evaluable (all will be positive for clinical symptoms).
- Positive Cultures: subjects with treatment failure will be evaluable (all will have positive cultures).

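### The test the SAP names for resistant colonisation (Table 9) compares later carriage without using the child's own enrolment carriage, which is already collected

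*SAP*

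**What the plan says.** SAP 4.2.3 states that the endpoint c analysis "will consist of two-sample tests for differences between proportions, using a chi-square test at significance level of 0.05", with a reference to Table 9. Protocol 12.4 gives the general secondary test as two-sided ("using a two-sided chi-square test at significance level of .05").

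The Table 9 shell in SAP 7.1 is labelled as the secondary analysis for endpoint c. It has three visit blocks (enrolment, TOC, Day 24-30), six carriage rows in each, and a column of chi-square p-values.

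The same SAP section then turns to emergence: "These analyses will examine whether antibiotic resistance after enrollment emerges differently between the short course and standard of care arms". It describes Table 9 as "a summary of antibiotic resistance present at enrollment, TOC and Outcome Assessment among the per-protocol population". Emergent resistance is defined against the enrolment stool by three rules:
- The child "Had no antibiotic-resistant E.coli or K.pneumoniae at enrollment but one or both are now present".
- The child had one resistant organism at enrolment and the other has since appeared.
- The child "Had antibiotic-resistant E.coli and/or K.pneumoniae at enrollment, but have now developed resistance to new antibiotics in either organism".

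This indicator is compared by arm in Table 10, by agent in Table 11 and by subgroup in Table 17. It is modelled in Table 23, whose covariate rows are blank. Mixed-effects and GEE models are to be explored, again for emergence.

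On the data, Protocol 9.2.3.1 says: "A stool specimen to determine antimicrobial resistance will be collected at all three study visits". Under Protocol 8.2 the enrolment visit falls on Day 2-6, before study product starts on Day 6.

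**The concern.** Protocol 2.1 argues that long courses lead to prolonged colonisation with "antibiotic resistant *E. coli* that may persist for months". If carriage persists like that, enrolment carriage should predict later carriage, and a comparison that leaves it out carries avoidable variance. The enrolment stool is a legitimate baseline covariate because both arms take the originally prescribed antibiotic through Day 5.

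The secondary objective in Protocol 4.1 concerns the number of children with resistant colonisation, and the rationale concerns prolonged colonisation. Emergence covers only part of this. A child who carries the same resistant organism with the same resistance pattern from enrolment to Day 30 meets none of the three rules, and neither does a child who clears it. Any effect of the shorter course on persistence or clearance therefore has to be read from Table 9, and no planned model of carriage uses baseline.

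**Working it through.** **The plan's own figure.** The documents give no power, carriage rate or effect size for endpoint c. The only sample-size figure is for the primary endpoint. It reproduces: (1.645 + 1.282)² × 2 × 0.05 × 0.95 / 0.05² ≈ 326 per arm. It says nothing about colonisation, so every carriage rate below is an assumption.

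**Variance removed by adjustment.** Let p be the proportion carrying at enrolment, a and b the later carriage in carriers and non-carriers, and m = pa + (1−p)b. The share of variance explained is p(1−p)(a−b)² / [m(1−m)].
- Weak link (p = 25%, a = 40%, b = 15%): m = 0.2125; 0.01172/0.16734 = 7.0%. Equivalent to 1/(1−0.070) − 1 = 8% more children.
- Middle (25%, 60%, 10%): m = 0.225; 0.04688/0.17438 = 26.9%. Equivalent to 37% more children.
- Strong link (30%, 80%, 8%): m = 0.296; 0.10886/0.20838 = 52.2%. Equivalent to 109% more children.

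**What that means for power.** Take 300 children per arm and later carriage of 24% v 16%. These arm rates are a further assumption, not derived from the three cases above. The crude standard error is √[(0.24×0.76 + 0.16×0.84)/300] = 0.0325, so power ≈ Φ(0.08/0.0325 − 1.96) = 69%.
- With 26.9% of the variance removed, the standard error is 0.0325 × √0.731 = 0.0278 and power is 82%.
- Simulation of a Mantel-Haenszel analysis stratified by enrolment carriage gave 79-84%, against 69-70% crude, over several splits of the effect between carriers and non-carriers.
- If the whole effect lies in baseline carriers (60% v 28%, with 12% of non-carriers in both arms), the stratified variance is [0.25(0.24 + 0.2016) + 0.75 × 2 × 0.1056]/300 = 0.000896. The crude variance is 0.001056, so the reduction is 15% and power is Φ(0.08/0.0299 − 1.96) = 76%.

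**Validity.** In 8,000 simulated trials with no effect, the crude test rejected in 4.8% and the stratified test in 4.6%.

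**Does the emergent indicator make Table 9 redundant?** Take 326 per arm, 20% carriage at enrolment, 15% acquisition and 70% persistence in the standard arm, with emergence counted by the first rule only.

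| Effect of short course | Later carriage | Crude carriage | Adjusted carriage | Emergent indicator |
|---|---|---|---|---|
| Halves acquisition only | 26% v 20% | 44% | 59% | 76% |
| Acquisition and persistence both × 0.7 | 26% v 18.2% | 67% | 77% | 33% |

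Over a wider grid (enrolment carriage 10-40%, acquisition 10-20%, persistence 40-80%), the emergent indicator had the most power in every acquisition-only scenario: 45-92%, against 12-83% for crude carriage and 18-87% for adjusted carriage. When persistence was also reduced, it fell below even crude carriage: 18-48% against 36-88%. The two tables answer different questions.

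**The case against.** The strongest objection is that the SAP already uses the enrolment stool. A reader who stops at the Table 9 shell might infer that the plan ignores that stool. It does not: the emergent definition in SAP 4.2.3 is built on it, child by child, and Tables 10, 11, 17 and 23 follow from it. The SAP's stated hypothesis is about emergence, the outcome measure in Protocol 4.2.1 speaks of children becoming colonised, and Table 9 is called a summary. For an effect on acquisition alone, the emergent indicator outperforms adjusted carriage. All of that stands.

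It does not dispose of the point. The SAP still ties its named test to Table 9, and the shell still prints p-values for post-enrolment carriage. Persistence is part of the protocol's rationale, and emergence cannot measure it.

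Two further objections also stand. An unadjusted test of a randomised comparison is valid, so the omission is not an error. And stratifying on four carriage levels by eight randomisation strata at two sites would make 4 × 8 × 2 = 64 cells for about 652 children, which is too sparse. The remedy has to be simpler.

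**Conclusion.** The point holds for the post-enrolment rows of Table 9. The test named for endpoint c leaves out a baseline value that was collected before the arms diverged, in the one planned comparison where persistence or clearance can show. Under assumed rates, adjustment would remove about 7% to 52% of the variance. Confidence is high that the adjustment is absent and moderate on its size.

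Three stronger readings are not supported:
- That endpoint c as a whole disregards baseline. The emergent definition contradicts this.
- That a large share of power is certainly lost. The documents give no rates, and the low end of the range is small.
- That chance baseline imbalance produces false positives beyond the nominal level. The crude test keeps its Type I error.

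Table 10 is also unadjusted, but adjusting it for enrolment carriage would remove only 0-7% of variance under the rates tried, so it is not part of the complaint. This is a free improvement of lower severity.

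**What to change.** In SAP 4.2.3 and the Table 9 shell:
- For the TOC and Day 24-30 rows, replace the crude chi-square with a Mantel-Haenszel risk difference stratified by enrolment carriage of that row's phenotype (yes/no). A logistic model with enrolment carriage, site, fever and antibiotic as main effects would also serve. Report it with a 95% confidence interval; the shell now gives only p-values.
- Keep the enrolment block as description and drop its p-values.
- State whether Table 9 or Table 10 decides endpoint c.
- Reconcile the Table 9 population: the text of SAP 4.2.3 says Population 4, while the shell says Population 2.

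Adjusting Tables 10-11 for the randomisation factors is optional and should gain little. The cost is SAP wording and programming, with no new samples or visits.

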Subjects that are diagnosed with a UTI while on study treatment and prior to the TOC Visit (between Day 6 and Day 11-14 TOC Visit) will be considered treatment failures and do not have to return for the TOC Visit but they will be asked to return for the Day 24-30 Outcome Assessment Visit and receive the Day 38-44 phone call. Similarly, subjects that are diagnosed with a UTI at any time after the TOC Visit through the Day 38-44 call will continue to return for the Outcome Assessment Visit and receive the Day 38-44 follow-up phone call. A stool specimen will still be collected at the Outcome Assessment Visit for these subjects diagnosed with UTIs (either before or after TOC).

Sub-studies

Seattle Children’s Hospital R21

An R21-funded sub-study titled, “Differences in infecting and colonizing Enterobacteriaceae from short-course vs. standard therapy of pediatric UTI” is being performed with collaborators at Seattle Children’s Hospital. This sub-study hypothesizes that both the antibiotic agent and the length of therapy will affect the patients’ indigenous flora and thus affect both the likelihood of recovering *E. coli* and/or *K.*

pneumoniae from stool and the resistance phenotypes of the recovered isolates. The sub-study will utilize PCR- and sequence-based methods to characterize phylogenetic and resistance properties of the recovered isolates.

Carbapenem resistant enterobacteriaceae

For each enrolled research subject, the stool or perirectal swab collected at the Test of Cure visit will also be utilized to perform additional screening for the presence of carbapenem resistant enterobacteriaceae. The results of this additional screening will be used to determine the prevalence of colonization with carbapenem-resistant Enterobacteriaceae (overall and for specific pathogens) in ambulatory children after completion of treatment for UTI.

Microbiome pilot study

For each subject at CHOP who agrees to participate in the Microbiome pilot study, an additional perirectal swab and anal swab will be collected. The additional swabs will be collected at each visit and will be used to determine the composition of the subjects' microbiome. For subjects in diapers, an additional stool swab will also be collected. The accuracy of microbiome analysis resulting from perirectal swabs will be tested via comparison with analysis performed on stool specimens. The anal swab will be used to assess the presence of skin flora contamination in the peri-rectal swabs.

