5.1 Tables

▪ Definition of populations

- **Population 1:** All subjects taking at least one dose of study treatment between Day 6 and Day 10 who have been evaluated for treatment success at TOC or have failed prior to TOC (ITT population)
- **Population 2:** The enrolled subjects who were adherent to their assigned study regimen and completed more than 80% of the prescribed dose between Day 6 and Day 10 (per-protocol population)
- **Population 3:** Subjects in population 2 who did not experience a treatment failure.
- **Population 4:** Subjects in population 2 who have a stool sample at TOC visit. Some treatment failures will not have a sample collected at TOC because they failed prior to TOC. Treatment failures without the sample at TOC would be excluded from population 4.

▪ Definition for a subject having primary endpoint

The primary endpoint of this study is the proportion of children experiencing treatment failure (symptomatic UTI) at the TOC visit (Day 11-14).

▪ Data handling

- Treat blanks and “.” as missing unless specified otherwise.

6. References

1. [name] R, Chan E. A meta-analysis of randomized, controlled trials comparing short- and long-course antibiotic therapy for urinary tract infections in children. *Pediatrics*. May 2002; 109(5):E70-70.

7. Appendices

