Arm 1 Standard Course(reference)			
Arm 2 Short Course			
Covariates			

Interaction Term			

SAS tips: SCALE=NONE in the MODEL statement of the PROC LOGISTIC procedure to generate deviance and Pearson chi-square for goodness of fit test.

Table 20. Multivariable Logistic Regression Analysis for Asymptomatic Bacteriuria at the TOC visit (Population 2) (Secondary endpoint b)

	Odds ratio	95% CI	p -value
Arm 1 Standard Course(reference)			
Arm 2 Short Course			
Covariates			

Interaction Term			

Table 21. Multivariable Logistic Regression Analysis for Symptoms that may be related to a UTI prior to or at the TOC visit (Population 2) (Secondary endpoint d)

	Odds ratio	95% CI	p -value
Arm 1 Standard Course(reference)			
Arm 2 Short Course			
Covariates			

Interaction Term			

Table 22. Multivariable Logistic Regression Analysis for positive urine cultures prior to or at the TOC visit (Population 2) (Secondary endpoint e)

	Odds ratio	95% CI	p-value
Arm 1 Standard Course(reference)			
Arm 2 Short Course			
Covariates			

Interaction Term			

Table 23. Multivariable Logistic Regression Analysis for Risk of emergent colonization with any antimicrobial resistant E. coli or K. pneumoniae in Gastrointestinal Tract (Population 4) (Secondary endpoint c)

	Odds ratio	95% CI	p-value
Arm 1 Standard Course(reference)			
Arm 2 Short Course			
Covariates			

Interaction Term			

Table 23 specifications: Repeat the analysis at enrollment visit, TOC visit, and outcome assessment visit separately as Table 26a, Table 26b, and Table 26c.

Table 24. Detailed listing for all adverse events possibly/probably related to study drug

Study Arm	Subject ID	Adverse event description	Onset date	Severity	Duration	Relationship to medication	Outcome

Table 24A. Adverse events possibly/probably related to study drug by body system and treatment arm (number of subjects)

	Arm 1: Standard Course Total= xxx N (%)	Arm 2: Short Course Total= xxx N (%)	
Total number of subject with adverse events			
Body as whole			

Table 24B. Adverse events possibly/probably related to study drug by body system and treatment arm (number of adverse events)

	Arm 1: Standard Course Total= xxx N (%)	Arm 2: Short Course Total= xxx N (%)	
Total number of adverse events			
Body as whole			

Table 25. Adverse events possibly/probably related to study drug by treatment arm

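### The Day 24-30 emergent-resistance comparison is limited to children with a TOC stool, so Day 24-30 stools the protocol collects from children who failed before TOC go unused

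*SAP*

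**What the plan says.** SAP 4.2.3 describes endpoint c as "assessed through Outcome Assessment visit (Day 24-30") and tests it "using a chi-square test at significance level of 0.05". No power or sample size is given for it. Emergent resistance is a change from the enrollment stool, scored at TOC and again at the Outcome Assessment visit. Tables 10, 11 and 17 report both visits in Population 4, and Table 23 models the same outcome in that population.

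The formal definition of Population 4 in SAP 5.1 is "Subjects in population 2 who have a stool sample at TOC visit". Population 2, its parent, requires more than 80% of the Day 6-10 doses. SAP 5.1 adds that failures lacking a TOC stool are left out. On evaluability, SAP 4.2.3 says: "Generally, subjects with treatment failure will not be evaluable for colonization". It makes one exception, for a failure who completes the TOC visit, because a specimen then exists.

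Under the protocol, a child who fails before TOC need not attend TOC, and the interim visit that stands in for it takes no stool (Protocol 8.3). The Protocol Summary then states: "A stool specimen will still be collected at the Outcome Assessment Visit for these subjects diagnosed with UTIs (either before or after TOC"). Protocol 8.4 repeats that failures give a stool at that visit.

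Three other places bear on the same population:
- The SAP 4.2.3 sentence introducing Table 9 glosses the set as "excluding treatment failures with a sample at TOC (Population 4"), while the definition of emergence that follows has "Among Population 4 (per-protocol population excluding treatment failures without TOC sample").
- The Table 9 shell in SAP 7.1 is headed Population 2, where the text says Population 4.
- The Table 23 specification reads "Repeat the analysis at enrollment visit, TOC visit, and outcome assessment visit separately".

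**The concern.** A Day 24-30 comparison needs a Day 24-30 stool and, because emergence is a change, an enrollment stool. It does not need a TOC stool. Requiring one removes children who have the relevant specimen, and the removal is not random: it falls on children whose treatment failed before TOC. Those children are referred for treatment outside the protocol, so they are likely to have had extra antibiotic exposure before Day 24-30.

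Reducing resistance is the trial's rationale, and SAP 4.2.3 hypothesizes less emergent resistance with short course. If short course fails more often and re-treatment raises resistance, the rule removes more high-risk children from the short-course arm. The error would then favor the hypothesis.

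**Working it through.** **1. The plan's own figure.** The documents give no number for endpoint c, so the primary sample size serves only to set the scale. With 5% failure in both arms, a 5-point margin and one-sided 0.05, the size per arm is (z_0.95 + z_power)² × 2 × 0.05 × 0.95 / 0.05².
- 90% power: (1.645 + 1.282)² × 38 = 325.4, so 326, as in SAP Table 3.
- 80% power: (1.645 + 0.842)² × 38 = 234.9, so 235, as in SAP Table 2.

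The protocol's 672 evaluable children give 336 per arm, used below.

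**2. Who is lost at Day 24-30.**
- Failure before TOC, dose rule met: no TOC stool by design, Day 24-30 stool planned, outside Population 4.
- Non-failure with only the TOC stool missing: outside Population 4 under SAP 5.1. The gloss in the definition of emergence would not exclude this child, since it mentions only failures.
- Failure at TOC with a TOC stool: inside Population 4, and so counted at Day 24-30 as well.

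**3. Number of failures lost per arm** = 336 × failure rate × share of failures that come before TOC and pass the dose rule. The share is an assumption. Every such child is taken to give a Day 24-30 stool, so these counts lean high.

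| Failure rate | Share 25% | Share 50% | Upper bound (100%) |
|---|---|---|---|
| 5% | 4.2 | 8.4 | 16.8 |
| 10% | 8.4 | 16.8 | 33.6 |

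With 326 per arm the upper bounds are 16.3 and 32.6. The 5% is the SAP's expected standard-arm rate. The 10% is that rate plus the 5-point margin.

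**4. Non-failures lost per arm** = 336 × 0.95 × share lacking only the TOC stool. If that share is 2-10% (assumption), the result is 6.4 to 31.9.

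**5. Effect on the arm difference.** Let s be the proportion of an arm that is dropped failures, and D the excess risk of emergence in failures over non-failures. The shift is (s_short − s_standard) × D. Take failure rates of 10% and 5%, and D of 20 to 40 points (assumption).
- All failures dropped: 0.05 × 0.20 = 1 point, to 0.05 × 0.40 = 2 points.
- Share 25-50%: 0.05 × 0.25 × 0.20 = 0.25 point, to 0.05 × 0.50 × 0.40 = 1 point.
- Equal failure rates and shares: 0.

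For comparison, if emergence is 10% in each arm (assumption), the standard error of the difference is √(2 × 0.10 × 0.90 / 336) = 2.3 points.

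**The case against.** The dose rule takes many of these children out first. A child with a confirmed UTI during Days 6-10 stops study product, and more than 80% of five once-daily cefixime doses means all five. This stands: the TOC-stool rule is not the only cause of loss, and 17 and 34 are ceilings. A child who completes dosing and fails after Day 10 but before the TOC visit still passes Population 2 and is lost only through the TOC-stool rule.

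The bias is conditional and small. It needs unequal failure rates, the emergence rates have no source in the documents, and even the 2-point upper figure is below one standard error. This also stands.

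Excluding failures might be defended as separating the effect of course length from that of re-treatment. The SAP does not say so, and its rule does not do it: a failure diagnosed at TOC and then treated remains in the Day 24-30 comparison. What decides inclusion is whether a TOC stool exists.

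The Table 9 shell uses Population 2, which needs no TOC stool, so adherent failures' Day 24-30 results could appear there. That limits the loss to the emergent-resistance tables and shows that text and shell must be aligned.

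Three stronger readings are tempting, and the documents do not support them:
- A reader might infer that a child with no enrollment stool counts as emergent. The first criterion describes a state at enrollment, SAP 5.1 treats blanks as missing, and the protocol plans a baseline stool for every child. The gap is silence: no rule classifies such a child.
- A reader might infer that Population 4 is defined in opposite ways. One ambiguous phrase in SAP 4.2.3 points that way. SAP 5.1, the gloss in the definition of emergence and the TOC exception all keep failures who have a TOC stool.
- A reader might infer from Table 23 that emergence is to be analyzed at enrollment. The indicator is defined only at the two later visits, so that run is a clerical slip.

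**Conclusion.** The point holds for the Day 24-30 emergent-resistance comparison. Population 4 demands a TOC stool that the comparison does not need. It leaves out pre-TOC failures whose Day 24-30 stool the protocol collects, and non-failures who missed only the TOC stool. This runs against the SAP's own ground for evaluability, which is having a specimen.

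The loss of failures is at most about 17 per arm at 5% failure and 34 at 10%. It falls to 4-8 and 8-17 if 25-50% of failures come before TOC and pass the dose rule. Any understatement of short-course resistance depends on a higher failure rate in that arm and on more emergence after failure; at equal failure rates only samples are lost. The missing rule for absent enrollment results, the stray phrase before Table 9, the Table 9 label and the Table 23 enrollment run are drafting gaps to close in the same edit. The endpoint is secondary and the primary non-inferiority conclusion is untouched, but the plan should be changed.

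**What to change.** In SAP 4.2.3 and 5.1, define the emergent-resistance set separately for each visit: Population 2 children with an enrollment stool result and a stool result at that visit, whatever their failure status. State that a child without an enrollment result is unclassifiable and excluded.

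Then:
- Delete the sentence making failures generally non-evaluable for colonization, and the conflicting gloss in the sentence that introduces Table 9.
- Use the new set for Tables 10, 11, 17 and 23, and drop the enrollment run from Table 23.
- Make the Table 9 population the same in text and shell.
- State that the dose rule still applies, and add a sensitivity analysis in Population 1 with the same stool requirements, so that failures who stopped product early are also counted.

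The cost is SAP wording and programming, since the protocol already plans the stools and their testing. The small downside is that denominators will differ between TOC and Day 24-30 and must be shown for each visit.
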